4.3.9. By-Visit Endpoints

By-visit endpoints will be analyzed using observed data, unless otherwise specified. For observed data analyses, missing data will not be imputed and only the observed records will be included.

4.3.10. Adverse Events and Concomitant Medications

The following imputation rules for the safety analyses will be used to address the issues with partial dates. The imputed dates will be used to determine the treatment-emergent period. For adverse events with a partial date, available date parts (year, month, and day) of the partial date will be compared with the corresponding date components of the start date and end dates of the treatment-emergent period to determine if the event is treatment emergent. When in doubt, the adverse event will be considered treatment emergent by default.

The following rules will be applied to impute partial dates for adverse events:

- If start date of an adverse event is partially missing, impute as follows:
 - If both Month and Day are missing and Year = Year of parent study treatment start date, then set to parent study treatment start date, as long as adverse event end date is not prior to parent study treatment start date;
 - If both Month and Day are missing and Year \neq Year of parent study treatment start date, then set to January 1;

- If Day is missing and Month and Year = Month and Year of parent study treatment start date, then set to parent study treatment start date, as long as adverse event end date is not prior to parent study treatment start date;
- If Day is missing and Month and Year \neq Month and Year of parent study treatment start date, then set to first of the month;
- If start date is completely missing, set to parent study treatment start date, as long as adverse event end date is not prior to parent study treatment start date.
- If end date of an adverse event is partially missing, impute as follows:
 - If both Month and Day are missing, then set to December 31;
 - If only Day is missing, then set to last day of the month;
 - If end date is completely missing, do not impute.

When the start date or end date of a medication is partially missing, the date will be imputed to determine whether the medication is prior or concomitant (or both).

The following rules will be applied to impute partial dates for medications:

- If start date of a medication is partially missing, impute as follows:
 - If both Month and Day are missing, then set to January 1;
 - If only Day is missing, then set to the first of the month.
- If end date of a medication is partially missing, impute as follows:
 - If both Month and Day are missing, then set to December 31;
 - If only Day is missing, then set to last day of the month.

If start date or end date of a medication is completely missing, do not impute.

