- ^s Endometrial biopsies are to be performed per instructions in the parent study. See the Laboratory Manual for guidance on handling and shipping the biopsy sample to the central laboratory for analysis. An endometrial biopsy will have been performed at the parent study Week 24 visit for all patients who participated in MVT-601-3001 (see MVT-601-3001 protocol for details) and in some patients who participated in MVT-601-3002 (see MVT-601-3002 protocol for details).
- ^t Patients enter diary information on menstruation status and feminine product use daily starting on the day of the Week 24/Baseline Visit.
- ^u A venous blood sample (for hemoglobin) must be collected each time feminine products are collected to be sent to the central laboratory conducting the alkaline hematin assessment. The site must document the start and stop dates of the patient's menses corresponding to the collected feminine products.
- ^v Patients will take the first dose of the study drug for this study once daily starting with the Week 24/Baseline visit (taken at the visit). The first dose of study drug for this extension study must not be taken until all parent study Week 24 procedures such as laboratory tests have been completed. The last dose of study drug will be taken in the clinic during the Week 52/Early Termination visit.
- ^w Pregnancy test must be negative before the study drug dose is administered.
- ^x The patient will enter her response(s) into an electronic tablet device at the site.
- ^y Collect adverse events from the time that the first dose of study drug for MVT-601-3003 is administered. Adverse events with onset prior to the first dose of study drug for MVT-601-3003 should be reported as an adverse event in the parent study (MVT-601-3001 or MVT-601-3002). If events originating in the parent study are ongoing at the time of the first dose of study drug for MVT-601-3003, please see the Study Reference Manual for instructions for recording the follow-up status.
- ^z Adverse events are collected for both the parent study and for MVT-601-3003 at the Week 24/Baseline visit (see footnote v for further details).
- ^{aa} Patients whose menses have not resumed as of the Follow-up visit for whom there is no explanation for the lack of resumption (eg, medical procedure or medications) will be contacted again by telephone 3 (+0.5) months after the Follow-Up visit to determine if menses has resumed and questioned about factors that may affect resumption of menses.

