9.1. Adverse Events

Adverse events will be collected from the time of the first dose of open-label study drug through the safety follow up visit approximately 30 days after the last dose of open-label study drug (the end of extension treatment period), or the date of initiation of another investigational agent or hormonal therapy or surgical intervention or entering the MVT-601-035 study, whichever occurs first. Serious adverse events reported to the investigator after the safety reporting period should be reported to the sponsor if the investigator assesses the event as related to study drug.

The severity of all treatment-emergent adverse events will be evaluated by the investigator based on the National Cancer Institute's Common Terminology Criteria for Adverse Events (CTCAE) and will be coded to preferred term and system organ class using MedDRA 22.0 or higher.

A treatment-emergent adverse event is defined as any adverse event that occurs after administration of the first dose of parent study drug.

Adverse event summaries will be based on treatment-emergent adverse events in the parent and extension studies, unless otherwise specified. All adverse events in the parent and extension studies will be listed in by-patient listings.

The following tabular summaries that include the number and percentage of patients will be provided:

- Overview of adverse events;
- All adverse events;
 - By SOC and PT;
 - By decreasing frequency of PT;
 - By SOC, PT, and maximum severity;
 - Study drug-related per investigator by SOC and PT;
 - By time to onset, SOC and PT;
- Grade 3 or above adverse events;
 - By SOC and PT;
 - By decreasing frequency of PT;
 - Study drug-related per investigator by SOC and PT;
- Grade 2 or above adverse events;
 - By SOC and PT;
 - By decreasing frequency of PT;
 - By SOC, PT, and maximum severity;

- Study drug-related per investigator by SOC and PT;
- Adverse events leading to study drug withdrawal;
 - By SOC and PT;
 - By decreasing frequency of PT;
- Adverse events leading to dose interruption;
 - By SOC and PT;
 - By decreasing frequency of PT;
- Adverse events resulting in fatal outcome;
 - By decreasing frequency of PT;
- Serious adverse events;
 - By SOC and PT;
 - By decreasing frequency of PT;
 - By SOC, PT, and maximum severity;
 - By SOC, PT, and relationship to study drug;
- Adverse events of clinical interest (ALT or AST $\geq 3 \times$ ULN);
 - By SOC, PT, and maximum severity;
 - By decreasing frequency of PT.

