- Adverse events with first onset during the extension study;
 - By SOC and PT;
 - By decreasing frequency of PT;

Additionally, adverse event categories defined in [Table 12](#) will be summarized by decreasing frequency of PT.

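### The start-date imputation for adverse events in SAP 4.3.10 has no floor at the first extension dose, so new extension events can be dated before it

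*SAP*

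**What the plan says.** SAP 4.3.10 has five rules for an incomplete adverse-event start date.

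- Whole date missing: "If start date is completely missing, set to parent study treatment start date, as long as adverse event end date is not prior" to parent start.
- Only the year known, same year as parent start: "If both Month and Day are missing and Year = Year of parent study treatment start date, then set to parent study treatment start date", with the same end-date guard.
- Only the year known, a different year: "Year of parent study treatment start date, then set to January 1".
- Day missing, same month and year as parent start: parent start, again with the end-date guard.
- Day missing, any other month: the text compares with "Month and Year of parent study treatment start date, then set to first of the month".

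The stated purpose is this: "The imputed dates will be used to determine the treatment-emergent period". Section 9.1 anchors treatment emergence to the parent study: "A treatment-emergent adverse event is defined as any adverse event that occurs after administration of the first dose of parent study drug".

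Three planned outputs depend on when an event began. Section 9.1 lists a tabulation by time to onset and a table titled "Adverse events with first onset during the extension study". Section 9.1.8 plans an exposure-adjusted rate whose denominator is exposure among patients still at risk of a first occurrence.

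On recording, footnote y to the Schedule of Activities (Protocol 1.1, Amendment 1) starts collection under MVT-601-3003 at the first extension dose. It continues: "Adverse events with onset prior to the first dose of study drug for MVT-601-3003 should be reported as an adverse event" in the parent study. Protocol 7.2.1 gives the same starting point.

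**The concern.** The protocol fixes a lower bound for the onset of any new event recorded in the extension, namely the date of the first extension dose. SAP 4.3.4 defines that date as Extension Study Day 1, but 4.3.10 does not use it. The rules can therefore assign a date already known to be too early. The error runs one way, from extension time into parent-study time.

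The default in 4.3.10 that counts doubtful cases as treatment-emergent does not help. It settles whether an event is emergent relative to the first parent dose, not in which study period it began.

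The first-onset table is the only item in the 9.1 list whose title confines it to the extension. For Group C, time before the first extension dose is placebo time. An event lost from that table would be one that arose on relugolix with add-back but was dated to placebo.

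**Working it through.** The plan states no figure on this point, so there is nothing to reproduce. The check applies the five rules and counts how often a true extension onset receives a date before the first extension dose.

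**Inputs from the documents.** First extension dose on parent Study Day 169, that is 168 days after parent start, with a visit window of -10 to +20 days (Protocol 1.1). Extension treatment of 28 weeks = 196 days. Collection to about 30 days after the last dose: 196 + 30 = 226 days.

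**Assumptions not in the documents.** Parent starts uniform over a 365-day year; onsets uniform over a window of L = 196 or 226 days.

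**Whole date missing.** Every event goes to parent start, so 100% are dated before the first extension dose. On the nominal schedule each is at least 168 days too early.

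**Only the year known.** The event is moved when its onset falls in the same calendar year as the first extension dose, unless that dose was on 1 January. Averaged over the year:

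share = 1 - (L - 1)/(2 × 365) - 1/365

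- L = 196: 1 - 195/730 - 1/365 = 73.0%
- L = 226: 1 - 225/730 - 1/365 = 68.9%

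Only 19-30% of all year-only events land on parent start itself, depending on the visit window and L. The other moved events land on 1 January. The result depends strongly on the calendar: with a mid-month parent start and L = 226, the moved share is about 1% for a July start and 100% for August to November starts.

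**Only the day missing.** The event is moved only when its onset falls in the same calendar month as the first extension dose and that dose was not on the first of the month. For a month of m days, the qualifying pairs of dose day and onset day number m(m - 1)/2. Over a year:

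7 × 465 + 4 × 435 + 378 = 5,373; 5,373/365 = 14.72 days on average

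- L = 196: 14.72/196 = 7.5%
- L = 226: 14.72/226 = 6.5%

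None of these events goes to parent start, and the imputed date precedes the dose by at most 30 days. About 92-94% stay in the extension.

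A day-by-day enumeration of all parent starts and onsets gave the same shares. They did not change when the first extension dose was moved across the visit window. No event was dated before parent start.

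**Example.** Parent start 1 February 2018, first extension dose 19 July 2018.

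| Recorded start | Imputed start | Before first extension dose? |
|---|---|---|
| nothing | 1 Feb 2018 | yes |
| 2018 | 1 Feb 2018 | yes |
| July 2018 | 1 July 2018 | yes |
| September 2018 | 1 Sept 2018 | no |

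**Overall size.** The documents do not give the share of incomplete dates. If 1% to 5% of new extension events had one (an assumption), the share of all such events misdated would be:

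- all day-only: 0.01 × 6.5% = 0.065% to 0.05 × 7.5% = 0.375%
- all year-only: 0.01 × 68.9% = 0.69% to 0.05 × 73.0% = 3.65%
- all wholly missing: 1% to 5%

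**The case against.** Several points count against a strong version of this concern.

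**Not every rule points to the parent start.** A reader might infer that all incomplete dates are pulled back to the parent study. Only three of the five rules use the parent start. The other two take the earliest day of the recorded year or month, and a known month after that of the first extension dose keeps the event in the extension. This objection stands.

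**Loss from the first-onset table is not established.** The SAP gives treatment emergence as the purpose of the imputed dates and does not say how first onset in the extension is derived. It could be taken from the study in which the event was recorded, and then no event would leave the table. This stands, so the loss is conditional. It does not rescue time to onset or time at risk if those use imputed dates.

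**Placebo and relugolix rates are not being swapped.** A reader might infer that Group C events on active drug would be reported as a placebo rate. Section 9.1.8 counts exposure to any study drug across both studies, so the two periods are already pooled for Group C. An early date shortens that patient's time at risk; it does not move an event between two reported rates. No formal treatment comparisons are planned either.

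**Wholly missing dates should be rare.** Visits are about four weeks apart, and Protocol 10.1.6 requires event start and end dates in the source records. This is fair, and it limits the size.

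**A blanket floor could itself do harm.** Footnote y refers sites to the Study Reference Manual for parent-study events still ongoing at the first extension dose. That manual is not available here. If such events also appear on MVT-601-3003 forms, a floor applied to every record would turn parent-study onsets into false extension onsets. This stands and narrows the fix.

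**Conclusion.** The gap is real but narrow. For new-onset events recorded under MVT-601-3003, SAP 4.3.10 can assign a start date that the protocol's recording rule excludes: always for a wholly missing date, about 69-73% of the time for a year-only date, and about 6.5-7.5% for a missing day. The last two figures rest on uniform start and onset dates. The missing-day share would be higher if onsets cluster soon after the first extension dose.

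Time to onset is affected directly, and so is the time at risk in 9.1.8 if exposure is counted up to the imputed onset. The first-onset table is affected only if it is built from imputed dates, which the SAP leaves open. A reader might also infer that events are lost from the overall summaries. They are not, because emergence runs from the first parent dose and no imputed date in the check fell before it.

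The total effect is small under any plausible share of incomplete dates, but it is systematic, runs one way and is cheap to remove.

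**What to change.** Add one rule to SAP 4.3.10. For a new-onset adverse event recorded under MVT-601-3003, an imputed start date earlier than the first extension dose is set to the date of that dose, provided the recorded date parts and the end date allow it. Leave out follow-up entries of parent-study events that were ongoing at the first extension dose. Where the recorded parts place the onset before the dose, the floor does not apply and the record should be queried.

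Add one sentence to SAP 9.1 saying that first onset during the extension is determined from this date.

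The cost is two sentences and a short programming step, plus a way to identify carried-over parent events. Under the assumptions above, the share of new extension events dated before the first extension dose falls to 0% for each pattern of missing parts, and treatment-emergent totals stay as they are.

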5. STUDY POPULATION

5.1. Subject Disposition

The number of patients for each of the following categories will be summarized by parent study treatment group:

- All patients enrolled in the Extension Study;
- Patients included in the Extension Safety population;
- Patients who completed the 28-Week open-label treatment period;
- Patients who discontinued early from the 28-Week open-label treatment period and reasons for discontinuation;
- Patients who enrolled in study MVT-601-035.

5.2. Protocol Deviations

Protocol deviations that occurred during the extension study will be categorized as important or minor per the protocol deviation plan. Important protocol deviations will include, but will not be limited to, the following categories:

- Patient treated with open-label study drug who did not satisfy key entry criteria;
- Patient treated with open-label study drug who met withdrawal criteria during the study but was not withdrawn;
- Patient treated with open-label study drug who received a prohibited concomitant medication that met criteria for an important protocol deviation.

Important protocol deviations will be summarized by deviation category for all patients in the Extension Safety population. A patient listing of all important protocol deviations will be provided.

5.3. Demographic and Baseline Characteristics

Demographic and Baseline characteristics will be summarized by parent study treatment group assignment for the Extension Safety population. Categorical data will be summarized using frequencies and percentages, by parent study treatment group and overall (see [Table 8](#) below). Summaries of continuous data will display the mean, SD, median, minimum, and maximum. The numbers of missing values will also be summarized.

Table 8: Categories for Demographic and Baseline Characteristics

Variable	Category
Age (years)	< 40, ≥ 40
Geographic region	North America, Rest of World
Race	Black or African American, White, American Indian or Alaska Native, Asian, Native Hawaiian or Other Pacific Islander, Other
Ethnicity	Hispanic or Latino, Not Hispanic or Latino, or Not reported
BMI (kg/m ²) at Baseline	< 18.5, 18.5 to <25, 25 to <30, 30 to < 35, 35 to < 40, ≥ 40
History of prior pregnancy	Yes, No
Disease duration of uterine fibroid (years)	Min to <1, ≥ 1 to < 3, ≥3 to <5, ≥5 to <10, ≥ 10
Type of uterine fibroids	
Subserous fibroid	Yes, No
Intramural fibroid	Yes, No
Submucosal fibroid	Yes, No
Other	Yes, No
Any surgery for uterine fibroids	Yes, No
Volume of myoma at Baseline (cm ³)	< 25, ≥ 25
Volume of uterus at Baseline (cm ³)	< 300, ≥ 300
Menstrual blood loss volume at Baseline (mL)	< 225, ≥ 225
Menstrual blood loss volume at Baseline (mL)	< 160, ≥ 160
Hemoglobin at Baseline (g/dL)	Min to < 8, ≥ 8 to <10.5, ≥ 10.5 to <12, ≥ 12
UFS-QoL Bleeding and Pelvic Discomfort Scale	0 to < 25, 25 to <50, 50 to <75, 75 to 100
Maximum NRS score for uterine fibroid-associated pain at Baseline	< 4, ≥ 4
Patient Global Assessment	
Function	No limitation at all, Mild limitation, Moderate limitation, Quite a bit of limitation, Extreme limitation
Symptoms	Not severe, Mildly severe, Moderately severe, Very severe, Extremely severe

Abbreviations: BMI = body mass index; NRS = Numerical Rating Scale; UFS-QoL = Uterine Fibroid Symptom and Health-Related Quality of Life.

5.4. Medical History

Medical history collected at the time of entry into the parent study will be coded using the Medical Dictionary for Regulatory Activities (MedDRA) and will be summarized by system organ class (SOC) and preferred term (PT) for the Extension Safety population. Additionally, summaries of uterine fibroid-specific medical and surgical treatment history collected at the time of entry into the parent study will be provided. A patient with multiple occurrences of medical history within a PT will be counted only once in that PT.

5.5. Prior Medications and Concomitant Medications

Prior medications and concomitant medications taken during the parent and extension study treatment period will be summarized for all patients in the Extension Safety population by parent study treatment group. Medications are considered concomitant if exposure occurs during the parent or extension treatment period. Medications are considered prior if exposure started prior to the date of first dose of parent study drug.

The number and percentage of patients who took at least one dose of a prior medication for treatment of uterine fibroids will be summarized by parent study treatment group and overall using the World Health Organization (WHO) Drug Dictionary and summarized according to the Anatomical Therapeutic Chemical (ATC) Classification System and generic medication name. A patient who has been administered several medications with the same preferred medication name will be counted only once for that preferred medication name.

6. STUDY DRUG EXPOSURE AND COMPLIANCE

All analyses of extent of exposure to study drug and compliance will be summarized by actual treatment received in the parent study. Extent of exposure to relugolix and E2/NETA during the extension study will be summarized for patients in the Extension Safety population. Overall exposure to relugolix (with or without E2/NETA), overall exposure to E2/NETA, and overall exposure to any study drug (relugolix [with or without E2/NETA] and placebo) throughout the parent study and extension study will be summarized by parent study treatment group. Compliance with open-label study drug during the extension study for the Extension Safety population will be summarized by parent study treatment group. Overall compliance with study drug throughout the parent study and extension study will be summarized by parent study treatment group. Exposure to and compliance with relugolix and E2/NETA will be summarized separately and will be based on the drug accountability case report forms.

Study drug exposure summaries will include the total dosage of relugolix and E2/NETA taken in milligrams and treatment duration. Total dosage of relugolix and E2/NETA taken during the extension study and overall, throughout the parent and extension studies, will be summarized by parent study treatment group. Treatment duration during the extension study and overall with any study drug (relugolix, E2/NETA, or placebo) will be summarized by parent study treatment group.

Study drug compliance will be summarized for the extension study treatment period and for the overall parent and extension study treatment period, and will be calculated as follows:

$$(\text{total tablets taken} / \text{total tablets expected to be taken}) \times 100$$

The total tablets taken will be calculated as:

$$(\text{total tablets dispensed} - \text{total tablets returned})$$

The total tablets expected to be taken is calculated as the total number of tablets a patient is expected to take each day times the length of time (in days) that the patient was in the treatment period of the study. Tablets that were dispensed and not returned will be assumed to have been taken. For patients who did not return for their last scheduled visit, tablets that were dispensed and not returned will not be included in the calculation of study drug compliance. For patients who did not return for any extension study visits after week 24 and did not return dispensed extension study drug, extension study drug compliance will not be calculated and will be categorized as “not able to calculate” in summaries of extension study drug compliance.

Summary statistics of study drug compliance (eg, mean, median, etc.) will be presented, along with a categorical summary (eg, < 80%, 80% to 100%, > 100%).

